7.6 Study Schedule

			Follow-up								
Study activities	Preop	Surgery	0-6 days^	3 mo^. (± 2 mo.)	1 yr ^ (± 2 mo.)	2 yrs (± 3 mo.)	4 yrs (± 4 mo.)	5 yrs (± 6 mo.)	7 yrs (± 6 mo.)	9 yrs (± 7 mo.)	10 yrs (±3 mo.)
	Visit 1	Visit 2	Visit 3	Visit 4	Visit 5	Visit 6	Telep hone Visit 7	Visit 8	Visit 9	Telep hone Visit 10	Visit 11
Discuss study with subject	х										
Medical History review	х										
Eligibility and consent	х										
Physical Examination with Harris Hip Score (HHS)/ ROM	х			x	χ ^Ω	х		χ ^Ω	xΩ		χ ^Ω
Operative and components details		х									
EQ-5D-5L	х			Х	x	х		х	х		х
Oxford Hip Score (OHS)	х			х	х	х		х	х		х
Satisfaction with 4-point Likert-type scale				х	х	х		х	х		х
X-Ray views* as per SOC	х		х	х	xΩ	x		χΩ	χΩ		χΩ
Complications/ Adverse Events		х	х	х	х	х	х	х	х	х	х
Schedule next visit	х		х	х	X	х	х	х	х	х	
Telephone interview							х			х	

Table 1. Schedule of Events

Ω Optional at these time points

- ^ The Post Op visit between surgery and 2-year visit will be conducted in accordance with the surgeon's standard of care.
- * It is not considered a protocol deviation if Optional X Rays are not completed. These should be completed at the discretion of the surgeon.

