1.0 SYNOPSIS

Study Reference	CSP2021-10				
Study Title	Clinical, radiographic and patient-reported outcomes using MobiliT cup with ECiMa insert in primary total hip arthroplasty surgery.				
Protocol Version/Date	V1.1 dated 27 September 2022				
Study Sponsor	Corin Australia Pty Ltd				
Study Purpose & Description	This Post-Market Clinical Follow (PMCF) study will evaluate clinical performance and safety outcomes of primary total hip arthroplasty surgeries using MobiliT cup with Paragon or TaperFit stem over a ten-year period. Participants will be selected for recruitment into the study from the general population of patients requiring a dual mobility total hip arthroplasty surgery and considered suitable to be implanted with MobiliT cup with Paragon or TaperFit stem (Corin Ltd). After the surgery, participants will be required to return for follow up visits and radiographic controls at specific timepoints and complete questionnaires for a period of 10 years.				
Study Objectives	 Primary Objective Evaluation of hip functional performance from baseline to 2 years after surgery. Secondary Objectives Confirmation of safety of the study devices up to 10-year follow up (FU). Evaluation of clinical outcomes and range of motion from baseline to 10-year FU. Evaluation of hip functional performance from 2 to 10 years after surgery. Assessment of health-related quality of life from baseline to 10-year FU. Evaluation of implants stability via radiographic analysis to detect evidence of migration, subsidence or loosening of the components using standard weight-bearing AP and lateral views of the treated hip from baseline to 10-year follow-up. 				
Study Endpoints	Primary Endpoint Improvement of Oxford Hip Score (OHS) from baseline (preop) to 2 years after surgery.				

	Secondary Endpoints					

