4.2 Secondary Endpoints

Secondary endpoints include:

- Revision rate of the devices under assessment after surgery to 10-year FU.
- Kaplan-Meier survival rate up after surgery to 10-year FU.
- Incidence of intraoperative and post-operative adverse events (hip, study device or surgery related) including severity and outcome up to 10-year FU.
- Change of Harris Hip Score (HHS) from preop to 10 years after surgery.
- Change of OHS from 2 to 10 years after surgery.
- Change of EQ-5-DL from preop to 10 years with previous follow-ups.
- Patient's satisfaction after surgery using the 4-point Likert-type scale at each time-point.
- Rate of continuous, progressive and symptomatic periprosthetic radiolucent lines greater than 2mm from immediate postoperative (baseline) to 2 years.

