7.2 Clinical Assessment and Patient Reported Outcome Measures (PROMs)

The clinical assessment is performed before surgery, at 3 months, 1 year, 2, 5, 7 and 10 years after the surgery. Preoperative assessment is used as baseline values for score improvement.

Harris Hip Score

The Harris Hip Score (HHS) is a disease-specific scoring system originally intended as outcome score after arthroplasty surgeries that include the domains of function, pain, motion, and deformity 16. The HHS is considered a clinical outcome measure. The maximum score of the absolute HHS is 100 points. Pain domain contributes 44 points, function 47, ROM 5 and absence of deformity 4 points. Function is subdivided into gait and activities of daily living. Calculation of the ROM score includes splitting the motion into categories based on utility and then multiplying the degrees of motion with a given index factor. The index scores are then added and multiplied by a factor of 0.05 to obtain the final ROM score. The ROMs of the affected hip/joint will be measured with a standard goniometer.

Oxford Hip Score

Oxford Hip Score (OHS) is a patient-centred questionnaire that is designed to assess functional ability and pain from the patient's perspective. It is a short, twelve-item questionnaire developed for completion by patients undergoing THA and is extensively referenced in the Orthopaedic literature. The OHS has been demonstrated to be highly sensitive to change in patients undergoing primary THA.¹⁷ Each of the 12 questions on the Oxford hip score presents a score decreasing as the reported symptoms increase (ie. become worse). All questions are laid out with response categories denoting least (or no) symptoms being to the left of the page (scoring 4) and those representing greatest severity lying on the right-hand side (scoring 0). This method, when summed, produces overall scores running from 0 to 48 with 48 being the best outcome.

EQ-5D-5L

The EQ-5D-5L essentially consists of 2 pages: the EQ-5D descriptive system and the EQ visual analogue scale (EQ VAS).

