7.3 Radiographic evaluation

The radiographic evaluation includes standard X-rays such as antero-posterior (AP) of the pelvis/ hip and lateral views of the affected hip before surgery and then at discharge (0-6 days), and 2 years. Any X-Ray imaging done between 0-6 days and 1 year post op will be done as per Surgeon's SOC. At further follow-ups 1, 5, 7, 10 years, X-rays are optional and/or will be taken only in case of subjective complaints such as pain or clinical symptoms warrants more investigation.

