7.4 Survivorship Analysis

Survival analysis of the study devices is calculated with the use of Kaplan-Meier estimation and 95% confidence interval. The analysis will be performed with the following end points:

- Revision of the acetabular component due to dislocation
- Revision of the femoral and/or acetabular component due to failure of the stem (such as stem fracture)
- Revision of the femoral and/or acetabular component due to aseptic loosening
- Definite or probable radiographic evidence of loosening of the components (such as lysis).

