10.0 STATISTICAL CONSIDERATIONS

10.1 Statistical Methods and Data Analysis

The following describes the statistical analyses foreseen at the time of study planning. Detailed statistical methods will be described in a separate Statistical Analysis Plan (SAP).

Statistical analyses will be performed when data has been collected for the study population at 2 years, 5 years, and 10 years follow-up.

Descriptive statistics will be provided in summary tables according to the type of variable summarised:

- survivorship will be calculated as Kaplan-Meier analysis with 95% confidence interval.
- quantitative variables will be summarized by using n (sample size), arithmetic mean, standard deviation (SD), median, minimum, and maximum, comparing between follow-ups and baseline values (where applicable).
- categorical variables will be summarized by using frequency count and percent distribution. Additional analysis may include comparisons of interest across demographic and baseline characteristics.

The analyses will include:

Analysis of primary endpoint:

- Percent change and absolute improvement of OHS will be reported at each follow-up visit compared to pre-op and previous visit(s) using a repeated-measures t-test.

Analysis of secondary endpoints:

- The survival of the devices will be expressed as crude revision rates and 95% confidence intervals and include listing of details of revision procedures (reason, time to revision, components revised).
- Hip-/ procedure-/ device- related adverse events will be listed and summarized based on the different mechanisms of classification, such as type of event, timing (operative/post-operative), seriousness and relation with the study devices.
- Postoperative HHS compared to pre-op baseline and previous visits. Percent change and absolute improvement will be reported for total scores and/or sub-scores as appropriate.
- Postoperative EQ-5D-5L compared to pre-op baseline and previous visits. Percent change and absolute improvement will be reported for total scores and/or sub-scores (EQ-VAS) as appropriate.
- Patient's satisfaction with the results of the surgery and any change to previous visit.

 The rates and extent of any radiolucent lines, osteolysis and rates of implant loosening will be reported at specified follow-up time points, as assessed by available radiographs.

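### HHS/ROM and X-rays are not required after 2 years, yet one secondary endpoint, two objectives and one Kaplan-Meier end point depend on them to 10 years

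*Protocol*

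**What the plan says.** **Schedule.** In Table 1 (section 7.6), the row for physical examination with HHS/ROM and the row for X-rays both carry the mark "Optional at these time points" at 1, 5, 7 and 10 years. A footnote adds, for films only: "It is not considered a protocol deviation if Optional X Rays are not completed". Section 7.3 says that at those four visits "X-rays are optional and/or will be taken only in case of subjective complaints such as pain" or where clinical symptoms call for investigation. The synopsis, under Study Procedures, describes X-ray collection only as far as 2 years.

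**Claims to 10 years.** Section 4.2 lists as a secondary endpoint "Change of Harris Hip Score (HHS) from preop to 10 years after surgery". The synopsis objectives include clinical outcomes and ROM to 10 years, and implant stability on radiographs "from baseline to 10-year follow-up". Section 7.4 lists four Kaplan-Meier end points, the last being "Definite or probable radiographic evidence of loosening of the components". Section 4.2 runs Kaplan-Meier survival to 10 years.

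**Other relevant text.** Section 7.2 says: "The clinical assessment is performed before surgery, at 3 months, 1 year, 2, 5, 7 and 10 years after the surgery", with no mention of an option. Section 10.1 reports radiolucent lines, osteolysis and loosening "as assessed by available radiographs". The one radiographic secondary endpoint in section 4.2, on radiolucent lines, stops at 2 years.

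**The concern.** The objectives, one endpoint and one survival end point promise 10-year results from assessments that the schedule does not require after 2 years. A statistical analysis plan can say how missing values are handled. It cannot supply examinations and films that nobody was asked to obtain, so this is not something a later document can settle.

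The results at stake are 10-year HHS change, ROM and radiographic stability. Section 3.4 says the study will support the MDR submission and publications on mid- and long-term performance and safety. If those results come from whichever patients happened to be examined or filmed, they do not describe the enrolled hips, and assessments not done at 5, 7 or 10 years cannot be recovered.

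There is also a plain conflict for sites. Section 7.2 says the clinical assessment is done at every listed visit, while Table 1 says HHS/ROM is optional at four of them. The deviation exemption in the Table 1 footnote names X-rays only, so a site cannot tell whether a missing 10-year HHS is a deviation.

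**Working it through.** **The plan's own figure.** The only calculated figure is in section 10.2: power above 0.90 for a paired t-test on OHS change to 2 years, with 100 hips, mean change 22.6, SD 9.8 and two-sided alpha 0.05. The standardised change is 22.6 / 9.8 = 2.306, and the noncentral t distribution gives power of about 1.00, so the statement holds. It concerns OHS at 2 years and says nothing about 10-year HHS or radiographs.

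**Requirement against claim.**

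| Result | Last required assessment | Claimed horizon |
|---|---|---|
| HHS change (4.2) | 2 years (Table 1) | 10 years |
| ROM (synopsis objective) | 2 years (Table 1) | 10 years |
| Radiographic stability (synopsis objective) | 2 years (7.3, Table 1) | 10 years |
| Radiographic-loosening Kaplan-Meier end point (7.4) | 2 years (7.3, Table 1) | 10 years, via 4.2 |
| Radiolucent lines (4.2) | 2 years | 2 years |
| OHS (4.2, Table 1) | 10 years | 10 years |

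The first four rows do not match; the last two do. The 1-year option matters little, because both assessments are required at 2 years. Section 7.7 widens the later gap. It encourages site attendance up to Visit 6 (2 years) and lets patients who cannot attend complete questionnaires at home, but ROM is measured with a goniometer (section 7.2) and cannot be obtained that way.

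**Loosening rate among filmed hips.** The true rates and imaging probabilities here are assumptions, not protocol figures. Let p be the true rate, s the chance that a loose hip is filmed, and a the chance that another hip is filmed. The rate among filmed hips is p·s / (p·s + (1 − p)·a). With s = 0.9:

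- p = 2%, a = 0.5: 0.018 / (0.018 + 0.490) = 3.5%
- p = 2%, a = 0.1: 0.018 / (0.018 + 0.098) = 15.5%
- p = 5%, a = 0.5: 0.045 / (0.045 + 0.475) = 8.7%
- p = 5%, a = 0.1: 0.045 / (0.045 + 0.095) = 32.1%

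**Loosening over all hips.** The rate found is p·s. If half the hips are filmed regardless of loosening (s = a = 0.5), a true 2% is found as 0.02 × 0.5 = 1%. The two summaries can therefore err in opposite directions.

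**Precision.** With no loosening seen among n filmed hips, the upper limit of the two-sided 95% exact interval is 1 − 0.025^(1/n): 3.6% for n = 100, 7.1% for n = 50 and 16.8% for n = 20.

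**HHS, direction of bias.** Assume 20% of patients are symptomatic with mean HHS 70 and the rest have mean 95. The true mean is 0.2 × 70 + 0.8 × 95 = 90.0.

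- Symptomatic patients examined with probability 0.9, others 0.3: the symptomatic share of those examined is 0.18 / (0.18 + 0.24) = 0.429, and the observed mean is 84.3.
- Probabilities reversed: the share is 0.06 / (0.06 + 0.72) = 0.077, and the observed mean is 93.1.

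The sign depends entirely on who is examined, which the protocol does not say.

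**The case against.** The strongest reply is that little of the study depends on this. The primary endpoint is OHS at 2 years. OHS, EQ-5D-5L and satisfaction are required at 5, 7 and 10 years, and adverse events are collected throughout. The radiolucent-line endpoint and the synopsis X-ray procedures already stop at 2 years. The synopsis calls the analysis descriptive, and an HHS bias of a few points is small beside the rise of 93.7 − 41.1 = 52.6 points in the sponsor's French study (section 3.1). All of this stands, and it limits the severity.

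The conflict with section 7.2 can also be softened. That section covers HHS and the questionnaires together, and section 7.7 says follow-up visits are performed as Table 1 sets out, so Table 1 can be taken to govern. This settles which text a site should follow, but leaves the endpoint and objectives without required data.

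Three stronger readings are tempting, and the documents do not support them:

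- A reader might infer that late HHS/ROM data are symptom-driven. The complaint trigger in section 7.3 and the surgeon-discretion footnote to Table 1 concern X-rays only. Fitter patients might equally be the ones who attend.
- A reader might infer that an unfilmed hip will be counted as not loose. Section 7.4 states no censoring rule, section 10.1 leaves detailed methods to a separate plan, and films are scheduled for all hips at 0–6 days and 2 years. The possible loss is of silent loosening after 2 years.
- A reader might think that censoring each hip at its last radiograph solves the problem. After 2 years only hips that are filmed again would stay in the risk set. With symptom-triggered films that censoring is informative, and it carries the same selection into the curve.

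**Conclusion.** The point holds as a mismatch between schedule and claims: 10-year HHS change, ROM, radiographic stability and radiographic loosening are claimed, and none has a required assessment after 2 years. This rests on the text alone.

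For HHS/ROM, the late results would describe a discretionary subset and the direction of bias is unknown. For radiographs, selection is partly by symptoms. Rates among available films then tend to be too high, by an amount that depends on imaging practice (2% read as 3.5% to 15.5%, or 5% as 8.7% to 32.1%, on the stated assumptions), while a curve over all hips could miss silent loosening. These figures show possible size and are not predictions.

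It should be fixed, but it is not critical: the primary endpoint, the patient-reported outcomes, revision and adverse-event capture, and the radiolucent-line endpoint are untouched.

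**What to change.** Reconcile the synopsis (objectives and procedures) with sections 4.2, 7.2, 7.3, 7.4, 7.6 (Table 1) and 10.1. Specifically:

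- Limit the HHS endpoint, the clinical/ROM objective, the radiographic-stability objective and the radiographic-loosening Kaplan-Meier end point to 2 years, the last visit at which both assessments are required.
- Report later HHS/ROM and films descriptively only, as number assessed over number at risk with the reason for assessment, and label them as a selected subset.
- Let OHS, required at 5, 7 and 10 years and already an endpoint from 2 to 10 years, carry long-term function. Let the revision end points in section 7.4 carry 10-year survivorship.
- Align section 7.2 with Table 1, and state whether a missing optional HHS is a deviation.

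This adds no visit, examination or film. The cost is a protocol amendment, which needs HREC approval under section 11.4, and the loss of a formal 10-year HHS or radiographic claim, which the present schedule cannot support.

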This visit will occur 0-6 days from the date of surgery while the patient is still at the hospital. Standard of care assessments will be performed which include X-rays of the treated hip. Postoperative pain management will be under the decision of the orthopaedic surgeon and support staff who will provide instructions to the patients regarding home care during the first few weeks after surgery. Medications are often prescribed for short-term pain relief after surgery. The rehabilitation program will depend on patient's goals and desired activities according to the SOC at the site. The goal of physical therapy intervention during the early post-operative phase is to decrease swelling, increase range of motion, enhance muscle control and strength in the involved lower extremity and maximize patients' mobility with a goal of functional independence.

Rehabilitation program may be individualized in function of bone quality, age, health and physical fitness of the patient. Any substantial changes to the SOC rehabilitation program will be documented. Immediate post-op complications/AEs related to the hip, or the surgery will be recorded. Any Serious Adverse Event (SAE) related to the treated hip and/or device-related incident will be recorded and reported to the Sponsor as per guidelines.

Follow Up Visits 4, 5, 6, 8, 9 and 11

The follow-up visits will be performed per the Schedule of Events table (Table 1). The study participants will be encouraged to attend site visits up to Visit 6 within the scheduled visit window to complete study assessments and questionnaires. X-rays of the treated hip will be completed as

per the schedule. When participants are unable to visit the study sites physically, participants will be encouraged to complete study questionnaires at home and provide any relevant complications/ Adverse Events information via email. When a study patient is unable to visit the study site as per the schedule of events, a protocol deviation will be reported with justification and a description of the corrective action plan to prevent a future occurrence.

Telephone Interview – Visit 7 and 10

At this contact, a designated delegated team member will telephone the participant to enquire about any complications. Any Adverse or Serious Adverse Event (SAE) or device-related incident will be recorded and reported to Corin as per guidelines. The participant will be reminded about the 10-year FU visit.

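### The schedule makes the Harris Hip Score and range-of-motion examination optional at 1, 5, 7 and 10 years, although change in HHS to 10 years is a secondary endpoint and ROM to 10 years a secondary objective

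*Protocol*

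**What the plan says.** Four parts of the protocol bear on this point.

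- **Endpoint.** Section 4.2 lists "Change of Harris Hip Score (HHS) from preop to 10 years after surgery" as a secondary endpoint. The synopsis does the same.
- **Objective.** The secondary objectives in the synopsis include "Evaluation of clinical outcomes and range of motion from baseline to 10-year FU".
- **Text on assessments.** Section 7.2 states: "The clinical assessment is performed before surgery, at 3 months, 1 year, 2, 5, 7 and 10 years after the surgery". HHS, with ROM measured by goniometer, is described directly below, and nothing there says that any of these visits is optional.
- **Schedule.** In Section 7.6, Table 1, the row "Physical Examination with Harris Hip Score (HHS)/ ROM" has a plain mark before surgery, at 3 months and at 2 years. At 1, 5, 7 and 10 years it carries the symbol Ω, explained as "Optional at these time points".

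Section 7.7 runs the follow-up visits according to Table 1 and adds: "The study participants will be encouraged to attend site visits up to Visit 6 within the scheduled visit window". On analysis, Section 10.1 plans "Postoperative HHS compared to pre-op baseline and previous visits".

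**The concern.** Because Section 7.7 makes Table 1 the operative schedule, a site could follow it exactly and record no HHS or ROM after 2 years. The endpoint and objective would then have no data at the time point that defines them, and no analysis plan can recover an examination that was never done.

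The likelier outcome is partial collection. Some sites may examine everyone, some no one, and some only the hips that attend or that give cause for an examination. The protocol does not say which. If troublesome hips are examined more often, late HHS reads too low. If mainly fit patients attend, it reads too high. The result feeds a regulatory clinical evaluation, where a 10-year functional score would be read as describing the enrolled cohort.

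**Working it through.** **1. The passages side by side (HHS/ROM)**

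| Visit | Section 7.2 | Table 1 |
|---|---|---|
| Pre-op | performed | required |
| 3 months | performed | required |
| 1 year | performed | optional |
| 2 years | performed | required |
| 5 years | performed | optional |
| 7 years | performed | optional |
| 10 years (endpoint) | performed | optional |

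After 2 years, 0 of 3 scheduled examinations are required. The OHS, EQ-5D-5L and satisfaction rows carry no optional mark at any of these visits. The defect follows from this table alone and needs no numerical assumption.

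**2. The plan's own figure**

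The protocol gives no precision or power for HHS or ROM. Its only such figure is for OHS at 2 years (Section 10.2): mean change 22.6, SD 9.8, two-sided alpha 0.05, 100 hips, power above 0.90. The standardised effect is 22.6/9.8 = 2.31. A paired t-test with 100 hips then has power above 0.999, and 5 hips already give 0.96. The claim reproduces, but it says nothing about late HHS.

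**3. Precision of the pre-op to 10-year change (illustration)**

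Inputs from the sponsor's French study in Section 3.1: HHS 41.1 (SD 17.7) before surgery and 93.7 (SD 8.8) at 2.5 years. The change is 93.7 - 41.1 = 52.6 points. Assumptions: these SDs hold at 10 years; the correlation r between the two scores is 0 to 0.3; 60 hips are still followed; either all of them or 30% (0.30 × 60 = 18) are examined.

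- SD of change = √(17.7² + 8.8² - 2r × 17.7 × 8.8) = 19.8 at r = 0 and 17.2 at r = 0.3.
- 95% half-width = t × SD/√n.
- n = 60 (t = 2.00): 4.5 to 5.1 points.
- n = 18 (t = 2.11): 8.6 to 9.8 points.

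In the widest case the interval is 52.6 ± 9.8, or 42.8 to 62.4.

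**4. Bias from selective examination (illustration)**

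Assume that 10% of hips score 70 and 90% score 94. The true mean is 0.1 × 70 + 0.9 × 94 = 91.6. With examination probabilities a (poor hips) and b (good hips), the observed mean is (0.1a × 70 + 0.9b × 94)/(0.1a + 0.9b).

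| a | b | Observed mean | Bias |
|---|---|---|---|
| 0.9 | 0.4 | 40.14/0.45 = 89.2 | -2.4 |
| 0.9 | 0.2 | 23.22/0.27 = 86.0 | -5.6 |
| 0.4 | 0.9 | 78.94/0.85 = 92.9 | +1.3 |

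More generally, the bias has size (1 - f) × gap, where f is the share examined and gap is the mean difference between examined and unexamined hips. For a 10-point gap it is 2.5, 5.0 or 7.5 points at f = 75%, 50% or 25%. For a 5-point gap it is 1.25, 2.5 or 3.75. Enrolling more hips does not reduce it.

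**5. Smaller late changes (illustration)**

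Suppose that the SD is 8.8 at both 2 and 10 years with r = 0.5. The SD of the 2- to 10-year change is √(8.8² + 8.8² - 2 × 0.5 × 8.8²) = 8.8. The 95% half-width is then 2.5 points with 50 hips and 4.1 with 20. A selection bias of up to 5.6 points, as in step 4, exceeds either, so a late drift of a few points could be hidden or invented.

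**The case against.** The strongest reply is that the consequence is limited. HHS is secondary, the study calls itself descriptive, and optional late examination suits a non-interventional design that follows standard of care where possible (Section 3.5). HHS is required at 2 years, and OHS, which covers patient-reported function and pain, is collected at 5, 7 and 10 years. All of this stands and lowers the severity. It does not remove the mismatch: OHS does not measure range of motion, and if optional collection is intended, the endpoint's horizon should say so.

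It can also be argued that the sentence in Section 7.2 is only a visit calendar for the whole set of assessments, with Table 1 governing. That softens the conflict with Section 7.2, but the conflict with the 10-year endpoint remains.

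Three stronger readings are tempting, and the documents do not support them.

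- A reader might infer that the surgeon decides which hips are examined. The footnote on discretion, "It is not considered a protocol deviation if Optional X Rays are not completed. These should be completed at the discretion of the surgeon", is worded for X-rays. For HHS/ROM no decision-maker is named.
- A reader might infer that only HHS/ROM is affected. The X-ray row carries the same mark at the same visits.
- A reader might infer that the 10-year objective cannot be answered. On the illustrative figures, a half-width of 9.8 and a bias of 5.6 are small beside 52.6 points.

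How the comparison with previous visits treats missed examinations may properly be left to the statistical analysis plan and is not part of this point.

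**Conclusion.** The point holds as an inconsistency between the schedule and the stated endpoint and objective. No HHS/ROM examination is required after 2 years, so late results would rest on hips selected by no stated rule, whether through site practice, attendance or clinician choice.

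The expected cost is lower precision (roughly double the half-width if 30% rather than all of 60 hips are examined) and a possible bias of unknown direction, a few points in the examples. The large gain over the pre-operative score would probably still show. Smaller late changes and ROM would be unreliable. These sizes depend on assumed follow-up, examination rates and score distributions, and on 2.5-year SDs from another cohort. The protocol gives no expected examination rate.

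The primary endpoint is unaffected. Severity: should be fixed.

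**What to change.** Reconcile Table 1 with Sections 4.2 and 7.2 and the synopsis, in one of two ways.

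- **(a) Keep the 10-year horizon.** Remove the optional mark from the HHS/ROM row at least at 10 years, so that the examination is recorded at every attended visit where it is required. Report the number examined out of the number still followed. The cost is a short examination at visits already scheduled. This will not close every gap, because site attendance is actively encouraged only up to the 2-year visit.
- **(b) Keep the examination optional.** End the HHS endpoint and the ROM objective at 2 years, the last visit at which the examination is required, and qualify Section 7.2 to match. Present later HHS and ROM only descriptively, with the number examined out of the number followed. The cost is a shorter stated horizon.

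Either option changes one table row or a few lines of text, but it is a protocol amendment and needs sponsor and investigator agreement and ethics committee approval under Section 11.4. It is best made before the late visits fall due, since missed examinations cannot be recovered.
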